8.3.5 ADVERSE EVENT REPORTING

The PI [name] will review all protocol data at monthly meetings, including enrollment and retention statistics and aggregate reports of side effects/AEs. [name] will be the responsible one to report any individual occurrence of an AE to the Chair of the DSMB according to the guidelines established at the initial DSMB meeting (e.g., the DSMB may require the reporting of any serious adverse event on an individual basis and in an on-going fashion). She will also report all severe AEs to the IRB and DSMB within 1 week. Since we are employing a marketed pharmaceutical product (i.e., a non-IND study), unexpected Severe AEs will also be reported to the FDA MedWatch Program. The NIMH program officer will be notified of any study modifications or suspension imposed by the DSMB or local IRB in response to an AE.

8.3.6 SERIOUS ADVERSE EVENT REPORTING

[name] will also report all AEs graded as severe to Investigator [name]. [name] will maintain a secured, password protected file linking subject ID to subject name. [name] will also receive the randomization code by subject ID from Investigational Drug Services. If it is medically necessary to become unblinded to treatment assignment, [name] will be able to do so very quickly.

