8.3.2 DEFINITION OF SERIOUS ADVERSE EVENTS (SAE)

An adverse event (AE) or suspected adverse reaction is considered "serious" if, in the view of either the investigator or sponsor, it results in any of the following outcomes: death, a life-threatening adverse event, inpatient hospitalization or prolongation of existing hospitalization, a persistent or significant incapacity or substantial disruption of the ability to conduct normal life functions, or a congenital anomaly/birth defect. Important medical events that may not result in death, be life-threatening, or require hospitalization may be considered serious when, based upon appropriate medical judgment, they may jeopardize the participant and may require medical or surgical intervention to prevent one of the outcomes listed in this definition.

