8.3.3 CLASSIFICATION OF AN ADVERSE EVENT

8.3.3.1 SEVERITY OF EVENT

The following guidelines will be used to describe severity of AEs.

- **Mild** – is defined as having no effect on activities of daily living such as transient light headedness or sweating with venipuncture; breast tenderness, mild skin irritation; or something of equal significance that requires no medical intervention and is of marginal clinical relevance.
- **Moderate** – would be associated with temporary (minutes to a few days) disruption in activities of daily living such as temporary loss of consciousness with venipuncture; a worsening of migraines or headache that require bed rest, an increase in anxiety or anhedonia symptoms consistent with clinically meaningful levels, emergent suicide intent without specific plan (severity level 4 on the C-SSRS), excess sleepiness or fatigue that resolves with additional rest, or something of equal significance.
- **Severe** – would cause serious disruption in daily activities of living and may or may not require hospitalization. Examples of such events would include a thromboembolic event, breast carcinoma, an increase in blood pressure consistent with Stage 2 hypertension, any cardiovascular event, any event that is permanently disabling, any event requiring hospitalization or is life threatening, severe mood impairment or emergent suicide ideation with specific plan (severity level 5 on the C-SSRS) or any suicidal behavior (actual attempt, interrupted attempt, aborted attempt, or preparation towards imminent suicide attempt), or something of equal significance. The development of endometrial hyperplasia with or without atypia would also be consistent with a severe AE.

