8.4.2 UNANTICIPATED PROBLEM REPORTING

The investigator will report unanticipated problems (UPs) to the reviewing Institutional Review Board (IRB) and to the Data Coordinating Center (DCC)/lead principal investigator (PI). The UP report will include the following information:

- Protocol identifying information: protocol title and number, PI's name, and the IRB project number.
- A detailed description of the event, incident, experience, or outcome.
- An explanation of the basis for determining that the event, incident, experience, or outcome represents an UP.
- A description of any changes to the protocol or other corrective actions that have been taken or are proposed in response to the UP.

To satisfy the requirement for prompt reporting, UPs will be reported using the following timeline:

- UPs that are serious adverse events (SAEs) will be reported to the IRB and to the DCC/study sponsor within 1 week of the investigator becoming aware of the event.
- Any other UP will be reported to the IRB and to the DCC/study sponsor within 1 week of the investigator becoming aware of the problem.
- All UPs should be reported to appropriate institutional officials (as required by an institution's written reporting procedures), the supporting agency head (or designee), and the Office for

Human Research Protections (OHRP) within the timeline in accordance with policy of the IRB's receipt of the report of the problem from the investigator.

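### Expedited safety reporting in 8.3.5 and 8.3.6 is triggered by the grade severe, not by the 8.3.2 definition of serious, which leaves a narrow gap for serious events graded below severe

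*Combined protocol and SAP*

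**What the plan says.** Section 8.3.2 defines seriousness by outcome and adds a limb that rests on medical judgement: "Important medical events that may not result in death, be life-threatening, or require hospitalization may be considered serious" if they may jeopardise the participant and may need intervention to prevent a listed outcome.

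Section 8.3.3.1 grades severity as mild, moderate or severe. The severe grade is itself partly based on outcome, since it takes in "any event that is permanently disabling, any event requiring hospitalization or is life threatening". The moderate grade covers short-lived disruption of daily life and lists, among its examples, suicide intent without a specific plan (C-SSRS level 4).

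The routine reporting duties use the grade:

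- Section 8.3.5, IRB and DSMB: "She will also report all severe AEs to the IRB and DSMB within 1 week".
- Section 8.3.5, FDA: "unexpected Severe AEs will also be reported to the FDA MedWatch Program".
- Section 8.3.6, headed as the section on serious adverse events: a study role "will also report all AEs graded as severe" to an investigator.

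Two places do mention serious events. Section 8.3.5 says, as an example, that the DSMB may ask for individual, ongoing reports of any serious event under guidelines agreed at its first meeting. Section 8.4.2 says "UPs that are serious adverse events (SAEs) will be reported to the IRB and to the DCC/study sponsor within 1 week", a period that runs from when the event comes to the site's notice.

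**The concern.** Serious and severe are different attributes. The first describes an event's outcome or the threat it poses; the second describes its intensity. The protocol defines the first carefully and then does not use it as the trigger for any routine report to the IRB, the DSMB or MedWatch. An event that meets 8.3.2 but is graded moderate therefore falls outside those duties.

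What is at stake is how soon independent oversight learns of such an event. This matters most for suicidality. The trial recruits across the full range of anxiety and anhedonia symptoms, and section 10.1.6 names emergent suicidal intent among the events the DSMB is to monitor.

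**Working it through.** No arithmetic applies. The check maps the 8.3.2 outcomes to the 8.3.3.1 grades, then follows what is left through each reporting route.

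**Step 1. Which serious outcomes can be graded below severe?**

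| Outcome in 8.3.2 | Treatment in 8.3.3.1 | Can it fall below severe? |
|---|---|---|
| Death | Not named | No. Mild means no effect on daily life, and moderate means disruption lasting at most a few days |
| Life-threatening | Named as severe | No |
| Hospitalisation | Named as severe (prolongation not listed separately) | No |
| Incapacity | Permanent disability named; the general test for severe is serious disruption of daily activities | Lasting incapacity: no, as it exceeds the moderate time frame |
| Congenital anomaly | Not named | Possible but remote: pregnancy is an exclusion and 8.3.9 tests women under 55 before randomisation |
| Important medical event | Not named | Yes |

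The realistic remainder is the important medical event.

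**Step 2. Is there a concrete candidate in the protocol's own text?** Yes. Section 8.3.3.1 places C-SSRS level 4 suicide intent in the moderate grade. For emergent suicide ideation with intent, section 8.3.4 requires withdrawal from the study and breaking of the blind, with an escort to the emergency department if immediate treatment appears necessary. Section 7.2 also requires removal. An investigator could readily judge such an event to be an important medical event under 8.3.2. The catch-all for events of equal significance does not raise it to severe: that clause appears in all three grades, and this event is expressly listed as moderate.

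**Step 3. Which routes catch a serious event graded moderate?**

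| Route | Trigger | Recipient | Deadline | Catches it? |
|---|---|---|---|---|
| 8.3.5, main sentence | Severe | IRB, DSMB | 1 week | No |
| 8.3.5, MedWatch | Unexpected and severe | FDA | None stated | No |
| 8.3.5, DSMB guidelines | Whatever the DSMB asks for | DSMB Chair | None stated | Only if the DSMB so decides |
| 8.3.6 | Severe | An investigator | None stated | No |
| 8.4.2 | Unanticipated problem, any grade | IRB, DCC/sponsor, with onward reporting | 1 week to IRB and DCC/sponsor | Only if also an unanticipated problem; DSMB not named |
| 10.1.6 | Periodic review | DSMB | Every six months, or more often if the DSMB specifies | Yes, at the review |

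Under 8.4.1 an unanticipated problem must be unexpected, at least possibly related to the research, and suggestive of greater risk than was known. A suicidal crisis judged unrelated to participation would not qualify. The remaining steps for moderate events in 8.3.4 and 8.3.5 (immediate notice within the study team, re-evaluation within one week, monthly review by the principal investigator) are internal.

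**Result.** For a serious event graded below severe:

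- DSMB: no deadline fixed by the protocol.
- IRB: one week if it is an unanticipated problem, otherwise no deadline.
- MedWatch: no requirement, where the event is unexpected and would have been reported had it been graded severe.

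**The case against.** The strongest reply is that the severe grade already does most of the work of the seriousness definition. That stands. Hospitalisation, life threat and permanent disability are named as severe, and death or lasting incapacity cannot fit the lower grades. In places the severe grade is wider than 8.3.2: it brings in endometrial hyperplasia without atypia and Stage 2 hypertension.

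A second reply is that other routes exist. That stands in part. Section 8.4.2 gives a one-week IRB deadline for any unanticipated problem, whatever its grade, and the DSMB may set its own rule. But the first route is conditional and does not name the DSMB, and the second is optional and undated.

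A third reply is that judging an important medical event is as discretionary as grading severity. This is true, and changing the trigger will not remove judgement. It would direct that judgement to the question that 8.3.2 asks.

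Some stronger readings are tempting, but the documents do not support them:

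- A reader might list the 8.3.2 outcomes that the severe text does not name and infer that reporting of a death could wait six months. Step 1 rules this out.
- A reader might infer that the DSMB would see these events only at its six-monthly reviews. Section 8.3.5 allows it to require individual reports, and 10.1.6 allows more frequent review.
- A reader might take fainting at venipuncture, which is listed as moderate, as the typical missed event. It is described as temporary, and nothing shows that it would meet the jeopardy test in 8.3.2.
- A reader might infer that expected serious events are wrongly kept from MedWatch. The MedWatch sentence covers only unexpected events, and the change proposed here keeps that limit.
- A reader might see a missing MedWatch deadline as what separates serious from severe. No deadline is stated even for severe events; what differs is whether a report is required at all.

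**Conclusion.** The concern holds in a narrow form. Sections 8.3.5 and 8.3.6 key expedited reporting to severe and do not use the protocol's own definition of serious. The operative text is 8.3.5; the sentence in 8.3.6 concerns notice to an investigator, in a paragraph that goes on to unblinding.

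The gap is essentially the important medical event graded moderate, with congenital anomaly as a remote addition. For such an event the DSMB interval fixed by the protocol lengthens from one week to as much as six months, unless the board has set something shorter.

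Two assumptions underlie this: that an investigator would judge some moderate events, such as C-SSRS level 4 intent, to meet 8.3.2; and that not all of these would also be unanticipated problems. The documents give no expected event counts, so the number affected cannot be estimated. The efficacy analysis is untouched. The case for change is that the gap reaches suicidality and is cheap to close.

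**What to change.** 1. In 8.3.5, apply the one-week report to the IRB and DSMB to every adverse event that is serious (section 8.3.2) or severe (section 8.3.3.1). Keeping both terms means that no current report is lost.
2. In 8.3.5, apply the MedWatch sentence to unexpected adverse events that are serious or severe.
3. In 8.3.6, use the same trigger, so that the section matches its title.
4. Reconcile 8.3.2, 8.3.3.1, 8.3.5, 8.3.6 and 8.4.2, stating that seriousness is assessed separately from grade. In particular, state how an event that 8.3.3.1 lists as moderate, but for which 8.3.4 requires withdrawal and unblinding, is to be assessed for seriousness. That judgement belongs to the investigators and the DSMB.

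The cost is a few wording changes and probably a few more one-week reports. No treatment, visit or analysis changes.

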8.3.7 REPORTING EVENTS TO PARTICIPANTS

Not applicable.

8.3.8 EVENTS OF SPECIAL INTEREST

Not applicable.

8.3.9 REPORTING OF PREGNANCY

Since perimenopausal women may still become pregnant, especially those in the early menopause transition, we will assess pregnancy status by point of care urine pregnancy test for all participants under the age of 55. Pregnancy status will be tested via the use of urine hCG test (SA Scientific, San Antonio). Urine hCG is a rapid (results within minutes) qualitative test to detect the presence of hCG in urine to aid in the early detection of pregnancy. The SA urine hCG rapid test will be conducted in [name] lab using a small urine sample taken prior to the week 8 baseline laboratory session that precedes randomization to confirm that subjects are not pregnant. Women who are pregnant at this time will be withdrawn from the study. [name] lab has a CLIAA waiver certification from the NC Dept of Health to perform this assay at Carolina Crossing which expires September 02, 2021.

8.4 UNANTICIPATED PROBLEMS

8.4.1 DEFINITION OF UNANTICIPATED PROBLEMS (UP)

The Office for Human Research Protections (OHRP) considers unanticipated problems involving risks to participants or others to include, in general, any incident, experience, or outcome that meets all the following criteria:

- Unexpected in terms of nature, severity, or frequency given (a) the research procedures that are described in the protocol-related documents, such as the Institutional Review Board (IRB)-approved research protocol and informed consent document; and (b) the characteristics of the participant population being studied.
- Related or possibly related to participation in the research (“possibly related” means there is a reasonable possibility that the incident, experience, or outcome may have been caused by the procedures involved in the research); and
- Suggests that the research places participants or others at a greater risk of harm (including physical, psychological, economic, or social harm) than was previously known or recognized.

Corrective actions to be considered in response to an UP include:

- Modification of inclusion or exclusion criteria to mitigate the newly identified risks
- Implementation of additional safety monitoring procedures
- Suspension of enrollment of new participants or halting of study procedures for enrolled participants
- Modification of informed consent documents to include a description of newly recognized risks
- Provision of additional information about newly recognized risks to previously enrolled participants.

8.4.2 UNANTICIPATED PROBLEM REPORTING

The investigator will report unanticipated problems (UPs) to the reviewing Institutional Review Board (IRB) and to the Data Coordinating Center (DCC)/lead principal investigator (PI). The UP report will include the following information:

- Protocol identifying information: protocol title and number, PI's name, and the IRB project number.
- A detailed description of the event, incident, experience, or outcome.
- An explanation of the basis for determining that the event, incident, experience, or outcome represents an UP.
- A description of any changes to the protocol or other corrective actions that have been taken or are proposed in response to the UP.

To satisfy the requirement for prompt reporting, UPs will be reported using the following timeline:

- UPs that are serious adverse events (SAEs) will be reported to the IRB and to the DCC/study sponsor within 1 week of the investigator becoming aware of the event.
- Any other UP will be reported to the IRB and to the DCC/study sponsor within 1 week of the investigator becoming aware of the problem.
- All UPs should be reported to appropriate institutional officials (as required by an institution's written reporting procedures), the supporting agency head (or designee), and the Office for

Human Research Protections (OHRP) within the timeline in accordance with policy of the IRB's receipt of the report of the problem from the investigator.

8.4.3 REPORTING UNANTICIPATED PROBLEMS TO PARTICIPANTS

Corrective actions to be considered in response to an UP include:

- Modification of inclusion or exclusion criteria to mitigate the newly identified risks
- Implementation of additional safety monitoring procedures
- Suspension of enrollment of new participants or halting of study procedures for enrolled participants
- Modification of informed consent documents to include a description of newly recognized risks
- Provision of additional information about newly recognized risks to previously enrolled participants.

9 STATISTICAL CONSIDERATIONS

NOTE: There will not be a formal Statistical Analysis Plan (SAP) attached to this protocol. Rather, details on all analysis plans are to be found in this section under the specific subheadings. We will test whether there are any differences between related population means (time effect, within-subject) and whether mean levels change across time based on the treatment group the participants were randomized to (time x treatment effect, within and between-subject).

9.1 STATISTICAL HYPOTHESES

- Primary Efficacy Endpoint(s):
 - 1. Change in State-Trait Anxiety Inventory score [Time Frame: Baseline (Week 8), Weeks 16, 20 and 24]
 - H0: The mean scores of the State-Trait Anxiety Inventory are the same at baseline (week 8), and weeks 16, 20, and 24, both, in those randomized to active treatment and in those randomized to placebo.
 - H1: The mean scores of the State-Trait Anxiety Inventory will significantly change from baseline (week 8) to weeks 16, 20, and 24 in those randomized to active treatment, but not in those randomized to placebo.
 - 2. Change in SHAPS score [Time Frame: Baseline (Week 8), Weeks 16, 20 and 24]
 - H0: The mean scores of the SHAPS will not change from baseline (week 8) to weeks 16, 20, and 24, both, in those randomized to active treatment and in those randomized to placebo.
 - H1: The mean scores in the SHAPS score will significantly change from baseline (week 8) to weeks 16, 20, and 24 in those randomized to active treatment, but not in those randomized to placebo.
- Secondary Efficacy Endpoint(s):
 - 1. Change in AUC cortisol response [Time Frame: Baseline (Week 8), Weeks 16, 20 and 24]

- H0: The cortisol AUC will not change from baseline (week 8) to weeks 16, 20, and 24, both, in those randomized to active treatment and in those randomized to placebo.
- H1: The cortisol AUC will significantly change from baseline (week 8) to weeks 16, 20, and 24 in those randomized to active treatment, but not in those randomized to placebo.
- 2. Change in “threat bias” score from Dot Probe task [Time Frame: Baseline (Week 8), Weeks 16, 20 and 24]
 - H0: The mean score in the Dot Probe task will not change from baseline (week 8) to weeks 16, 20, and 24, both, in those randomized to active treatment and in those randomized to placebo.
 - H1: The mean score in the Dot Probe task will significantly change from baseline (week 8) to weeks 16, 20, and 24 in those randomized to active treatment, but not in those randomized to placebo.
- 3. Change in “hard choice” score from EEfRT [Time Frame: Baseline (Week 8), Weeks 16, 20 and 24]
 - H0: The mean score in the EEfRT task will not change from baseline (week 8) to weeks 16, 20, and 24, both, in those randomized to active treatment and in those randomized to placebo.
 - H1: The mean score in the EEfRT task will significantly change from baseline (week 8) to weeks 16, 20, and 24 in those randomized to active treatment, but not in those randomized to placebo.

9.2 SAMPLE SIZE DETERMINATION

Sample size calculations were performed for the primary outcome measures. Correlation and effect size estimations were based on previously published literature ^{173,174}. With a sample size of N=120 and performing hypothesis tests at two-sided alpha=.05 and a correlation of >.25 among repeated measures, we have >90% power to detect a small effect size of .15.

The G*power software was used to determine the sample size ¹⁷⁵, based on a repeated measures ANOVA with within-between interaction ^{173,174}. We conservatively account for 15% (n =18) withdrawal following randomization, yielding 138 women who complete the protocol (powered for 120). This sample size will provide sufficient power to address secondary endpoints. No exploratory analyses will be performed.

By using proc mixed (not GLM), we will apply an analysis which is relatively robust to missing data. Before applying proc mixed, we will check for the randomness of missing data.

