4.2 SCIENTIFIC RATIONALE FOR STUDY DESIGN

THIS IS NOT A CLINICAL EFFICACY TRIAL. However, we will employ an RCT design to study the pathophysiologic role of E2 variability [or levels] in the clinical symptoms of women in the MT. Under double-blind procedures, subjects will be randomized to receive 17 β - E2 or placebo for 16 weeks. The study biostatistician will create the randomization scheme and UNC Investigational Drug Services will manage the randomization and dispensing of hormones in blinded form. For those randomized to transdermal E2 (n=60), each will wear a patch (generic for Climara[®]) delivering 0.10 mg E2/24 hours. Those randomized to placebo (n=60), will wear a patch identical in appearance (3M Pharmaceuticals).

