6.3 MEASURES TO MINIMIZE BIAS: RANDOMIZATION AND BLINDING

Under double-blind procedures, subjects will be randomized to receive E2 or placebo for 16 weeks. The study biostatistician will create the randomization scheme and UNC Investigational Drug Services will manage the randomization and dispensing of hormones in blinded form. For those randomized to transdermal E2 (n=60), each will wear a patch delivering 0.10 mg E2/24. Those randomized to placebo (n=60), will wear a patch similar in appearance.

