9.3 POPULATIONS FOR ANALYSES

We will use an Intention-to-Treat (ITT) Analysis Dataset, including all randomized participants (either to transdermal estradiol patch and micronized progesterone pill, or placebo patch and placebo pill).

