9.4 STATISTICAL ANALYSES

9.4.1 GENERAL APPROACH

Descriptive statistics of continuous data will be presented as adjusted means (least squared means) and standard errors. A two-tailed p-value of $\leq .05$ will be considered as statistical significance.

Examinations of residual normality, linearity, homogeneity of variance, and influential outliers will be performed using the SAS Macro Mixed DX¹⁷⁶. Outliers at 2 SD's or more above or below the mean will be winsorized. For cortisol, the distribution of the values before and after every Trier Social Stress Test will be visually inspected and, in the case of skewness, a log-transformation will be performed.

We will use two-way repeated measures analyses with between-subject factors. Our models will test whether there is a mean value change in the primary and secondary outcomes from week 8 to weeks 16, 20, and 24 (within-subject analyses) and based on the treatment arm (between-subject analyses of transdermal estradiol vs. placebo treatment groups). We expect a significant change over time in the primary and secondary outcome measures in those randomized to active transdermal estradiol, but not in those randomized to placebo. Data will be analyzed using proc mixed in SAS. All models will use an auto-regressive covariance structure to account for the repeated assessments of primary and secondary outcomes in the same participants.

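### Section 9.2 calls 138 the number of completers, but 138 is 120 plus a 15% allowance and so a number to randomise; sections 4.2 and 6.3 randomise only 120.

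*Combined protocol and SAP*

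**What the plan says.** Section 9.2 sizes the trial with G*Power, using a repeated-measures ANOVA with a within-between interaction. For N = 120, two-sided alpha .05 and a correlation above .25 among the repeated measures, it claims "we have >90% power to detect a small effect size of .15". It then allows for loss: "We conservatively account for 15% (n =18) withdrawal following randomization, yielding 138 women who complete the protocol (powered for 120"). It adds that, by using proc mixed, "we will apply an analysis which is relatively robust to missing data".

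Two other sections give the number randomised. Section 4.2: "For those randomized to transdermal E2 (n=60), each will wear a patch", with another 60 on placebo. Section 6.3 repeats 60 for the active arm and says of the other arm: "Those randomized to placebo (n=60), will wear a patch similar in appearance". Both add to 120.

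Section 9.3 defines the analysis set as intention-to-treat, "including all randomized participants". The opening of section 9 says that no separate SAP will be attached, so no other planned document is named that could settle the number.

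**The concern.** The sentence in 9.2 attaches the wrong label to 138. An allowance for withdrawal takes the number needed at the end and raises it to a number to start with. Here the raised number is described as the women who finish.

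Sections 4.2 and 6.3 then use the number without the allowance. Either 120 women are randomised and the 15% allowance is lost, or 138 are randomised and the arm sizes in 4.2 and 6.3 are wrong. The reader cannot tell which. The randomisation list and the intention-to-treat set both depend on this number, and so does the claim of over 90% power, because 120 is the smallest total that reaches 90% at a correlation of .25.

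**Working it through.** **Inputs.** N = 120, alpha .05, correlation r above .25 (the floor of .25 is used), effect size .15, 15% withdrawal, 18 women, 138 women (all section 9.2); four visits, at weeks 8, 16, 20 and 24 (section 9.4.2); 60 + 60 randomised (sections 4.2 and 6.3). Section 9.2 does not name the effect-size metric. It is read here as Cohen's f, which is an assumption.

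**Step 1: reproduce the plan's power.** For the interaction with 2 groups and 4 visits, the noncentrality is λ = N × 4 × f² / (1 − r), with 3 and 3(N − 2) degrees of freedom. At N = 120:

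λ = 120 × 4 × 0.0225 / 0.75 = 14.4; df 3 and 354; power 90.2%.

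This agrees with the plan's claim of over 90%.

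**Step 2: where 138 comes from.** 0.15 × 120 = 18, and 120 + 18 = 138. It is the powered number plus 15% of itself.

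**Step 3: test each reading of the sentence.**

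| Reading | Randomised | Complete | Withdrawal |
|---|---|---|---|
| 138 randomised, 18 withdraw | 138 | 120 | 18/138 = 13.0% |
| 138 randomised, 15% withdraw | 138 | 138 × 0.85 = 117.3 | 15% (20.7 women) |
| 138 complete, 18 withdraw | 156 | 138 | 18/156 = 11.5% |
| 138 complete, 15% withdraw | 138/0.85 = 162.4, so 163 | 138 | 15% |
| 120 randomised (4.2, 6.3), 15% withdraw | 120 | 120 × 0.85 = 102 | 15% (18 women) |

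The last row fits both 15% and 18 women, but leaves 102 completers, not 138. No row combines 138 completers, 15% and 18 withdrawals. The documents mention neither 156 nor 163.

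**Step 4: power on completers only**, with f = .15, r = .25 and the formula of step 1, so that λ = 0.12 × N:

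| Completers | λ | Power | Correlation at which power is 90% |
|---|---|---|---|
| 120 | 14.40 | 90.2% | .246 |
| 119 | 14.28 | 89.9% | not computed |
| 117 (138 randomised, 15% loss) | 14.04 | 89.3% | .265 |
| 102 (120 randomised, 15% loss) | 12.24 | 84.3% | .361 |

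These figures follow the plan's sizing method: equal correlations and complete cases. They are not figures for the planned analysis, for which section 9.4.1 says "All models will use an auto-regressive covariance structure".

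**The case against.** The best defence is that the sentence in 9.2 nearly explains itself. It places the withdrawals after randomisation and gives 120 as the powered number, so the intended meaning is probably 138 randomised, 18 lost and 120 completing. On that reading the flaw within 9.2 is a slip of wording, plus the minor point that adding 15% is not the same as dividing by 0.85 (138 against 120/0.85 = 141.2, so 142). This is a fair reading of the intention. It does not remove the conflict with 120 randomised in 4.2 and 6.3.

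The second argument is that power hardly suffers. The plan assumes a correlation above .25. At .40, 102 completers give 91.9%. Section 8.2 quotes a test-retest intraclass correlation of 0.70 for the SHAPS, and at .70 the same 102 women give 99.8%. That coefficient comes from healthy participants, no retest interval is stated, and no equivalent is given for the STAI. The mixed model also keeps the visits that a woman completed before she withdrew. All of this stands as a limit on the size of the problem: the shortfall in step 4 applies near the .25 floor and to completers only. It does not tell the reader how many women will be randomised.

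Finally, sections 1.1 and 2.1 give 250 women. That is a study-population or recruitment figure. No section gives it as a number randomised, so it does not settle the question.

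**Conclusion.** The point holds. As written, 138 cannot be the number of completers given 15% and 18 withdrawals, and the plan does not say consistently whether 120 or 138 women are to be randomised. The count errors are plain arithmetic and rest on no assumption.

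The effect on power is modest and conditional. With f = .15, an equal correlation of .25 and completers only, power is 89.3% if 138 are randomised and 84.3% if 120 are, against the stated figure of over 90%. A correlation of about .27 or .36 respectively restores 90%. The mixed model recovers part of the loss, by an amount that depends on the effect pattern, the timing of withdrawal and the covariance structure; no figure is claimed for it. The plan's calculation at N = 120 is not in dispute.

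**What to change.** State one number randomised and use it in sections 4.2, 6.3 and 9.2. Replace the sentence in 9.2 with whichever of these applies:

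- 138 randomised (69 per arm); with 15% withdrawal about 117 complete; completers-only power 89% at correlation .25.
- 120 randomised (60 per arm); with 15% withdrawal about 102 complete; completers-only power 84% at correlation .25.

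In either case add that these are G*Power figures for f = .15 with equal correlations, and not for the planned auto-regressive mixed model.

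The cost is a text correction in three sections. Endpoints and analysis do not change, and the correction does not require more enrolment. If 138 is chosen, also check the randomisation list: section 6.3 says "The study biostatistician will create the randomization scheme", and the same section describes 60 per arm, so the list must provide for 69. Keeping 120 completers after a true 15% loss would take 142 randomised; that would be a design choice and is not needed to correct the text.
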